The risks of TEA are minor, including possible allergic response to the standard ECG electrodes. The likelihood of this risk is low, approximate incidence of $<1\%$. Since TEA uses current flow through the skin, there is a possibility of uncomfortable sensation or pain at the skin, abnormal or involuntary movements (chorea, dystonia, dyskinesia), gastrointestinal disturbances or nausea. However, the stimulation output will be set at a level that is well tolerated by the participant. In very rare occasions, the participant might experience rash or minor infection at the stimulation point that can be treated locally if needed. If this occurs, the device can be moved to the opposite leg at the same location. If the patient develops a local rash or minor infection in the opposite leg, the patient will discontinue the treatment and notify the study team. To protect subjects against risks, subjects will be instructed to avoid manipulating or rubbing the electrodes to avoid any electrode deformations or breakage. Subjects will be instructed to stop the TEA therapy immediately once they experience uncomfortable sensation or pain at the electrode site.

Participants may develop discomfort related to reporting daily symptoms and repeated surveys where they are asked about their health and well-being. In order to decrease this risk, the number of surveys have been prioritized to the most relevant surveys necessary to assess compliance. Finally, there is a risk for embarrassment from responding to the questionnaires, as many of the questions are pertaining to negative experiences such as pain, anxiety, depression, and quality of life. The participants will be allowed to skip question that cause them to feel discomfort.

Finally, there is a small risk of compromised confidentiality, which is associated with analysis and sharing of medical data. The likelihood of this risk is low, estimated to be $<1\%$. To reduce this risk, each subject will be assigned an ID number, and all data will be stored with the subject ID number only and not the subject's name. All data records entered into the study electronic data capture (EDC) system will be stored on the HIPAA- compliant cloud data server, which is

encrypted and password protected, and the EDC system will comply with the 21 CFR Part 11 requirements for electronic record keeping. All locally-stored data will be on a password-protected computer. Subject charts with medical history and assigned subject numbers will be kept in locked file cabinets stored at the clinical site. Access to charts will be granted only to study investigators. Charts will be kept confidential and will not be shared with any third parties without permission from the subject.

Patients who develop a serious adverse event (SAE), as defined by the Food Drug Administration (FDA) ²⁵, will have the study intervention discontinued, and be managed medically as deemed appropriate by the patient's clinical team. A SAE is defined by the FDA if the AE results in any of the following outcomes: death, a life-threatening AE, inpatient hospitalization or prolongation of existing hospitalization, a persistent or significant incapacity or substantial disruption of the ability to conduct normal life functions, or a congenital anomaly/birth defect. For related, unexpected, serious device events resulting in death and life threatening outcome (per IRBMED guidelines) these will be submitted as soon as possible but within 7 calendar days of becoming aware of the event.

The study team will submit to the reviewing IRB a report of any unanticipated adverse device effect occurring during an investigation as soon as possible, but in no event later than 14 calendar days after the investigator first learns of the effect.

7. Ethics and dissemination

TEA is similar to a transcutaneous electrical nerve stimulation unit that is classified by FDA as a non-significant risk device. Therefore, an investigational device exemption (IDE) for the FDA will not be needed.

The study will require approval by the IRB of the University of Michigan. Any protocol amendments will be communicated to the IRB. Informed consent will be obtained by the study coordinator face to face or by phone from eligible participants or authorized surrogates. If consent is obtained remotely, subjects will be sent a copy of the consent via mail and sign the consent virtually using eConsent or SignNow. Data will be captured in a password protected database. Each subject will be assigned a unique random number, and Protected Health Information will be de-identified after complete data extraction. The final dataset will only be accessible by the primary investigator and data analyst.

The final results may be presented at meetings, in publications, or in future funding applications; however, such presentations will be of aggregate data only without disclosure of any individual subject identities or PHI. The results of the trial will be posted in Clinicaltrials.gov. After study results are disseminated, deidentified participant data and the analytic code can be requested by external researchers to the principal investigator.

8. Timeline and feasibility

Over the past 3 years, the Comprehensive Pancreas Program of the University of Michigan has provided care to 314 new patients with CP or roughly 104 new patients per year. In addition, our program provides longitudinal care to patients with CP, resulting in 608 return visits for CP over the past 3 years or roughly 203 returns visits per year. Among these patients, it is expected that

87% have chronic abdominal pain.²⁶ [name] (CO-I), leads two research studies using TEA in patients with irritable bowel syndrome and diabetic gastroparesis as the University of Michigan (HUM00189911, HUM00217301).

Our proposed timeline is to complete the study in 12 months. This study will ensure feasibility of interventions, enrollment methods, and data collection tools. Results of this study will support a larger and longer study.

9. References

3. [name] JD, Chari ST, Timmons L, et al. A population-based evaluation of the natural history of chronic pancreatitis. *Pancreatology*. 2018;18(1):39-45. Epub 20171124.
4. [name] JD, Amann ST, Anderson MA, et al. Quality of Life in Chronic Pancreatitis is Determined by Constant Pain, Disability/Unemployment, Current Smoking, and Associated Co-Morbidities. *Am J Gastroenterol*. 2017;112(4):633-42. Epub 20170228.

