3. Non-English speaking patients
4. Scheduled for or with a history of pancreatic surgery (e.g. TPIAT, Puestow, Frey, Whipple, other)
5. Currently undergoing or about to start endoscopic therapy with ERCP or EUS
6. Recent history of acute pancreatitis as defined by the Revised Atlanta Classification within a month prior to enrollment
7. Radiologic and clinical findings consistent with symptomatic pseudocyst, wall-off necrosis, infected pancreatic necrosis, or biliary obstruction within the last 6 months
8. Self-reported daily use of opioids for > 12 months for weak opioids (codeine, tramadol and hydrocodone) or > 6 months for strong opioids (other opioids) in the last two years. A similar approach was used in a recent landmark RCT that compared endoscopic therapy vs. surgery in patients with painful chronic pancreatitis.¹⁹
9. Self-reported ongoing illicit drug use or abuse
10. Suspected or diagnosed pancreatic cancer
11. Receiving chemotherapy for cancer
12. Known allergy to adhesive ECG electrodes
13. Patients with bilateral below the knee amputation
14. Patients with lower extremity paralysis
15. Patients are participating in another clinical trial
16. Patients with an implantable electrical stimulation device.

Interventions

I. Run-in period: 2 weeks (V0)

After initial screening (V0 – virtual or in person) and after the consent form is signed, subjects that fulfill eligibility criteria will be invited to participate to the study.

All eligible subjects will then complete a pre-enrollment run-in period of 2 weeks. Over this run-in period, subjects will be asked to complete a diary with information on daily severity of abdominal pain. Subjects will rate their worst daily abdominal pain intensity over the past 24 hours by putting a mark on a visual analogue scale (scoring 0-10), where 0 represents “no pain” and 10 represents the “worst imaginable pain.” Subjects with abdominal pain severity of 4 or greater for at least 5 days in this run-in period will be invited for a site visit to start the intervention (V1). Subjects who don’t qualify for this criterion will not be invited to receive the intervention. A similar approach has been used in a prior RCT evaluating the role of antioxidants for pain in CP.²⁰ Surveys will be completed via RedCap.

II. Visit 1 (V1)

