In this initial visit, subjects will complete baseline questionnaires. This visit will either be in-person at the main hospital in Ann Arbor or performed remotely with the study coordinator. After enrolling in the study, subjects will be given the TEA device and receive instructions on how to use this via ST36. If the participant chooses to have the visit be remote, they will receive the study materials by mail prior to the visit and a pregnancy test supplied by the study team. In

either method of visit, the participant will be given a paid return mailer to give our supplies back. Participants will be subjected to a pregnancy test if they are of child-bearing potential on the day of V1. This will be done in the clinic or self-administered by the subject at home prior to the Zoom appointment. Recommendation to use some form of contraception during the study and birth control options will be discussed. Study participants will use the TEA device for 5 minutes under the supervision of the study coordinator. Subjects will be asked to start the intervention one day after the training received during the initial visit.

III. Home-based treatment period- 4 weeks

TEA will be self-administered at home over two daily treatment sessions of 30 minutes each. TEA will be performed using a device that measures about 4x6 cm (**Figure 2**), and that is programmed by the study team to deliver a specified weak electrical signal. The subject is able to adjust the stimulation output by pressing the “+” or “-“ sign on the device. The stimulation output is adjustable, because the tolerance level varies by individuals and settings will be adjusted based on maximal tolerance. The maximum current output is 10mA. All other parameters, including frequency, pulse width, and time on/time off during the pulsed stimulation, will be fixed. TEA is similar to a transcutaneous electrical nerve stimulation (TENS) unit that is classified by FDA as a non-significant risk device. The device is powered by a small rechargeable battery and the charging will take place only when the device is not in use. This device has been approved for use in two ongoing clinical studies at UoFM by the same investigation team (HUM00189911, HUM00217301).

[figure not shown]

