The treatment will be discontinued if the patient develops an adverse event (discussed under *6. Safety Management*) that requires the treatment to be stopped or at the participant request. Subjects will be allowed to start and continue conventional medical therapy for the duration of the study, including any pain medications. This will be at the discretion of the treating physician. This will allow us to assess the addition of TEA to conventional care. The TEA intervention will be discontinued if the patient gets admitted to hospital or if a surgical or endoscopic procedure is performed during the treatment phase of the study. During the 4 weeks of treatment, subjects will complete pain diaries through RedCap. This will take 2 minutes for completion.

IV. Monitoring phone calls

To assess any potential problems with the TEA device, we will contact participants via telephone within 72 hours of starting treatment and then weekly at 1 week, 2 weeks, and 3 weeks from treatment initiation.

V. Visit 2 (V2), 4 Weeks from V1

During this follow-up period subjects will complete the same set of surveys that was completed during the first visit to assess pain, quality of life, and anxiety or depression. Subjects will also return the TEA device using their return mailer (provided during or prior to visit 1). In the event the device is broken or non-functional, participants will still be requested to return the device.

VI. Visit 3 (V3), at 8 weeks from V1

After subjects finish treatment (4 weeks from V1), they will continue completing daily pain diaries for additional 4 weeks. During this phase, subjects will not receive device stimulation. At 8 weeks from V1, subjects will be asked to complete the same set of surveys completed during visit 1 and 2. These will be completed via RedCap.

VII. Close-out phone call, at end of trial

At the end of the trial, study subjects who enrolled and received TEA will be reached out via a phone call to assess on global impression and acceptability of the treatment.

Outcomes

Primary outcomes

1. Enrollment feasibility: how many patients with CP who are assessed meet eligibility criteria. In addition, of these, how many provide informed consent. Of those who consent, how many meet criteria to participate after the run-in period. Of those who meet run-in period criteria, how many start the intervention (TEA).

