8. Rates of hospital admission for pancreatitis-related hospital admissions [timeframe – 8 weeks from treatment onset]
9. Rates of treatment-related adverse events [timeframe - 4 weeks from treatment onset]
10. Patient global impression of change (PGIC) [timeframe: end of follow-up]: this is a 1-item question that should take less than 1 minute to complete. This question assesses the overall change on pain by using a 7-point Likert scale that ranges from (1) very much improved to (7) very much worse.
11. Modified abbreviated acceptability rating profile [timeframe: end of follow-up]: this is an 8-item questionnaire that should take 2 minutes (Tarnowski KJ, Simonian SJ. Assessing treatment acceptance: the Abbreviated Acceptability Rating Profile. *J Behav Ther Exp Psychiatry* 1992;23:101-6). Each item uses a 5-point Likert scale, including Strongly disagree, Disagree, Neutral, Agree, and Strongly agree. A final score ranges from 0-40, with 40 indicating the highest acceptability possible. This will serve to assess how study subjects perceive the acceptability of the TEA treatment for pain in CP.

Participant timeline

After enrollment, participants will have a 2-week run-in period, where they will complete daily pain diaries. If participants fulfill minimal pain requirements, participants will complete V1 to provide baseline data and will start TEA treatment. Participants will undergo TEA therapy twice a day for 4 weeks. During that time, participants will continue completing daily pain diaries and will 3 weekly phone calls to assess adverse events. After 4 weeks of TEA therapy, the participants will return the device and will complete V2, in which participants will complete questionnaires similar to V1. Participants will then continue completing daily pain diaries for additional 4 weeks, while not receiving the TEA therapy. At completion of those 4 weeks, participants will have closure V3, in which they will provide questionnaires similar to V1 and V2. The total participant's duration in the study is 10 weeks (2 weeks run-in, 4 weeks TEA treatment, and 4 weeks post TEA treatment assessment). At the end of the trial, participants will receive a close-out phone call to assess treatment acceptability.

Table 2: schedule of study visits

Visit ID	V0	V1	Phone call 1	Phone call 2	Phone call 3	Phone call 4	V2	V3 ^	Close-out
Target time	- 2 weeks	0	Within 72h	+1w	+2w	+3w	+4 weeks	+8 weeks	End of trial
Time window	2 weeks	+ 1 week					+ 1 week	+ 1 week	

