Procedure									
Eligibility evaluation	x								
Medical history and demographics	x								
Consent	x								
Pain diary (daily average & worse pain, weekly BPI-SF)	x	x					x	x	
Pain assessment (COMPAT-SF, opioids)		x					x	x	
Quality of life (PROMIS-29)		x					x	x	
Anxiety and depression (HADS)		x					x	x	
Adverse events			x	x	x	x	x		
Pancreatitis-related hospital admissions							x	x	
Patient global impression of change (PGIC)									x
Modified abbreviated acceptability rating profile									x

Recruitment

Participants will be identified using different methods. 1) We will use DataDirect to identify potential participants with chronic pancreatitis who do not have major exclusion criteria and who are actively following at the University of Michigan. This will provide a retrospective list of patients with chronic pancreatitis seen at the University of Michigan in the past 1 year. 2) The study coordinator will also identify potential participants from the list of patients scheduled for clinic visits with [name], [name], or other members of the pancreas clinic. This will be done using MiChart. 3) The study investigators (Drs. [name] and [name]) and physician colleagues seeing patients at the Comprehensive Pancreas Program will refer potential subjects to the study team. The research team will review potential study participants' medical history through the electronic medical record (MiChart) to assess patients' eligibility.

Once a subject is identified through any of the above methods, the subject will be contacted by phone using a phone script or approached in person in the outpatient clinic. The study team will follow a script and go through the pre-screen questions. If the patient is determined to be ineligible via the pre-screen questions they will be excluded from the study and logged as contacted by the study team but ineligible to participate. In doubt, the study investigator will

determine eligibility. If the subject meets eligibility criteria, the subject will be invited to participate in the study. If the subject is interested, an informed consent will be given either in person if the subject is in clinic or mailed for review & signature via eConsent or SignNow.

4. Methods: data collection

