All data will be collected using active and passive methods, including patient interviews, physical examinations, and review of electronic medical records. A trained research coordinator will collect data using standardized forms via RedCap. Research coordinators will follow the manual of operations for all study procedures. All forms will include essential instructions and definitions of variables.

A. Pre-screening form: this will include questions on inclusion and exclusion criteria, pertinent for study eligibility. Initial screening will be based on chart review, in person or telephone patient interview, endoscopic results, and radiologic data that are consistent with the study definition of CP. Screening data will be obtained by the research coordinator before enrollment. This is uploaded into section 8-1.8

B. Pain diary: this will be directly completed by patients. Daily pain scores will be recorded during the 2-week run in period. In those patients who are eligible and are started in TEA, patients will complete the pain diary for 4 weeks during the TEA therapy and will continue for 4 weeks after the intervention is over. The patients will report (a) average pain during the last 24 hours using a VAS, (b) maximal pain during the last 24 hours using a VAS, and (c) weekly BPI-SF (only after intervention started). The survey is uploaded into section 29.1.

C. Baseline form: this will include data on demographics, clinical profile of CP, laboratory biomarkers, radiologic findings, and prior therapeutic interventions, all of which will be recorded from the medical records and by patients filling up a survey. In addition, patients will complete a form pertaining to pain, quality of life, anxiety and depression using the instruments described in secondary outcomes.

D. First follow-up form: this form will be used to assess pain, quality of life, anxiety and depression after the intervention, using the instruments described in secondary outcomes. Adverse events of the intervention will also be recorded in this form. These surveys are uploaded into section 29.1.

E. Second follow-up form: This form will be given to participants during the first follow-up (V2). Subjects will be asked to complete and mail the follow-up questionnaires and diary. This form will be used to assess pain, quality of life, anxiety and depression after the intervention has been discontinued. These surveys are uploaded into section 29.1.

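### Enrollment is placed both before and after the run-in, so the acute pancreatitis exclusion has two end dates 14 to 21 days apart, and no full eligibility re-check is scheduled before the device is issued

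*Combined protocol and SAP*

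**What the plan says.** All references are to the combined protocol and SAP.

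- **Section 3, Eligibility criteria, exclusion 6:** "Recent history of acute pancreatitis as defined by the Revised Atlanta Classification within a month prior to enrollment".
- **Section 3, Interventions, I. Run-in period:** "All eligible subjects will then complete a pre-enrollment run-in period of 2 weeks". Enrollment comes after the run-in.
- **Section 3, Interventions, II. Visit 1:** "After enrolling in the study, subjects will be given the TEA device and receive instructions on how to use this via ST36". Enrollment again comes after the run-in, just before the device is handed over.
- **Section 3, Participant timeline:** "After enrollment, participants will have a 2-week run-in period, where they will complete daily pain diaries". Enrollment comes before the run-in.
- **Table 2:** the row "Eligibility evaluation" carries one mark, at V0. V1 falls two weeks later with a window of plus one week.
- **Section 4, item A:** "Screening data will be obtained by the research coordinator before enrollment". This inherits the same ambiguity.
- **Checks after V0:** the run-in rule, "Subjects with abdominal pain severity of 4 or greater for at least 5 days in this run-in period will be invited for a site visit", and a pregnancy test on the day of V1 for participants of child-bearing potential. The Participant timeline makes V1 and the start of TEA conditional on the pain requirement alone.
- **Section 5, Exploratory endpoints:** baseline worst and average pain are the run-in means, and the last week of treatment is compared with them.

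**The concern.** Several exclusions describe a state that can change within weeks: pancreatic surgery being scheduled (4), endoscopic therapy starting or imminent (5), acute pancreatitis (6), a symptomatic collection or biliary obstruction (7), and entry to another trial (15). If these are assessed only at V0, a patient can come to meet one before the device is issued, and no scheduled step would pick it up. Table 2 first records adverse events at phone call 1 and pancreatitis-related admissions at V2, both after V1.

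Acute pancreatitis is the sharpest case. Its pain can supply the five diary days at 4 or more, so an excluded event can help to qualify the patient. Those diary days are also the baseline. Recovery from the attack would then be read as improvement on TEA, and there is no control arm to show otherwise.

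The ambiguous anchor also affects a primary outcome. Whether a given patient counts as eligible in the enrollment-feasibility proportions depends on which meaning of enrollment the coordinator uses.

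**Working it through.** There is no plan figure to reproduce: the sample of 10 is given without a formula. The check is calendar arithmetic.

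**Inputs.** Run-in of 14 days (section 3, Interventions, I). V1 window of plus 7 days (Table 2). Look-back of one month, taken here as 30 days. Day 0 is V0, and the run-in is assumed to start at V0.

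**Gap between the eligibility evaluation and V1.** Minimum 14 days; maximum 14 + 7 = 21 days.

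**Days covered by exclusion 6:**

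| Meaning of enrollment | V1 on day 14 | V1 on day 21 |
|---|---|---|
| V0 (Participant timeline) | -30 to 0 | -30 to 0 |
| V1 (run-in and Visit 1 text) | 14 - 30 = -16, so -16 to 14 | 21 - 30 = -9, so -9 to 21 |

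**Consequences.**

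- An attack on day -20 is excluded under the V0 meaning and allowed under the V1 meaning. An attack on day +5 is allowed under the V0 meaning and excluded under the V1 meaning.
- Under the V1 meaning, an attack on day -12 is excluded if V1 takes place on day 14 (26 days earlier) and allowed if V1 takes place on day 21 (33 days earlier). It cannot be settled at V0.
- Under the V1 meaning, 14/30 = 47% to 21/30 = 70% of the look-back falls after the only scheduled evaluation. Under the V0 meaning, the whole 14 to 21 days before V1 lies outside the exclusion. Neither meaning comes with a scheduled check of those days.

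**Effect on the pain baseline.** If an attack raises the diary score by *d* points on 5 of the 14 run-in days and has resolved by the last week of treatment, that patient's run-in mean rises by 5*d*/14 = 0.36*d*. The mean change over 10 patients shifts by 0.036*d*. As the scale runs from 0 to 10, *d* cannot exceed 10, so five such days shift the patient's change by at most 3.6 points and the group mean by at most 0.36 points. A longer attack would shift both in proportion.

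**Effect on feasibility proportions.** With 10 starters, one patient is 1/10 = 10 percentage points of adherence or retention.

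**The case against.** The strongest reply is that the gap is mostly one of wording, and that a careful team would catch such a patient anyway. Section 5 defines the sample as subjects who meet eligibility and receive the device at V1. If enrollment means V1, exclusion 6 formally bars an attack during the run-in. Table 2 is not exhaustive, since it has no row for the V1 pregnancy test. The baseline form (section 4, item C) collects clinical profile, radiology and prior interventions, and may expose a recent event, although Table 2 puts medical history at V0 and the timing of that chart review is not stated. A manual of operations, not available here, may say more. Pain outcomes are exploratory, and the plan says that the study is underpowered for clinical outcomes.

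Much of this stands, and it rules out several stronger readings:

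- A reader might infer that eligibility is never checked after V0. It is: the pain-day count and the pregnancy test both come later.
- A reader might infer that the plan sends ineligible patients on to TEA. Nothing directs that a patient known to be ineligible receives the device. The documents support only that such a patient could start.
- A reader might see a loophole in the rule that stops TEA "if the patient gets admitted to hospital or if a surgical or endoscopic procedure is performed during the treatment phase of the study". That is a rule for stopping treatment, and no treatment is given in the run-in, so its limit to the treatment phase is natural.
- A reader might want a probability that one of the 10 is affected. The documents give no rate for these events. Any figure would reflect the assumed rate, and would describe the event occurring, not an ineligible patient going unnoticed and starting TEA.
- Any one patient among 10 moves a proportion by 10 points. That is not peculiar to this problem.

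The reply leaves two facts untouched: the text gives enrollment two positions, and the only scheduled full evaluation precedes V1 by two to three weeks.

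**Conclusion.** The contradiction is in the text and needs no assumption: enrollment stands on both sides of the run-in. The end date of exclusion 6 therefore moves by 14 to 21 days, and some patients get opposite decisions. Separately, apart from the pain-day count and the pregnancy test, no re-check of exclusions is scheduled between V0 and device issue. A patient who comes to meet exclusion 4, 5, 6, 7 or 15 in that interval could start TEA.

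The effect on results is possible rather than shown. Acute pancreatitis pain in the run-in could qualify a patient and inflate the baseline of an exploratory, uncontrolled comparison. The sizes above assume one such patient among 10, five affected diary days, and recovery by the last week of treatment; the exact dates assume a 30-day month. How often this would happen cannot be stated. The point is worth acting on because the remedy is small and changes what happens at V1. It does not undermine the design.

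**What to change.** 1. Reconcile the run-in text, the Visit 1 text and the Participant timeline to one definition of enrollment, and state which date anchors exclusion 6. The choice of date is the sponsor's.
2. Add a mark at V1 in the "Eligibility evaluation" row of Table 2. State in the Visit 1 text that the time-varying exclusions (4 to 7 and 15) are re-confirmed by interview and chart review before the device is issued, and before mailing when V1 is remote.
3. Report patients who fail the re-check, with the reason, at the existing fourth enrollment-feasibility proportion (those starting TEA out of those passing the run-in). No new outcome is needed.

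The scheduled gap between the last eligibility evaluation and V1 then falls from 14 to 21 days to none, or to the mailing time for a remote V1. The sample size is unchanged. The cost is a wording amendment, a few minutes at a contact that already takes place, and an occasional patient lost after completing the run-in.
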